	Grade 2 (Isolated AST or ALT >5.0×ULN and ≤8.0×ULN, if normal at baseline) (Isolated AST or ALT >2.0×baseline and ≤12.5×ULN, if elevated >ULN at baseline)	 Hold study drug/study regimen dose until Grade 2 resolution to Grade ≤1 or baseline. If toxicity worsens, then treat as Grade 3 or Grade 4. If toxicity improves to Grade ≤1 or baseline, resume study drug/study regimen after completion of steroid taper. 	 For Grade 2: Regular and frequent checking of LFTs (e.g., every 1 to 3 days) until elevations of these are improving or resolved. Recommend consult hepatologist; consider abdominal ultrasound, including Doppler assessment of liver perfusion. Consider, as necessary, discussing with study physician. If event is persistent (>3 to 5 days) or worsens, and investigator suspects toxicity to be immune-mediated AE, recommend to start prednisone 1 to 2 mg/kg/day PO or IV equivalent. If still no improvement within 3 to 5 days despite 1 to 2 mg/kg/day of prednisone PO or IV equivalent, consider additional workup and treatment with IV methylprednisolone 2 to 4 mg/kg/day. If still no improvement within 3 to 5 days despite 2 to 4 mg/kg/day of IV methylprednisolone, consider additional abdominal workup (including liver biopsy) and imaging (i.e., liver ultrasound), and consider starting immunosuppressives (i.e., mycophenolate mofetil).^a Discuss with study physician if mycophenolate mofetil is not available. Infliximab should NOT be used.

Table 3: Dosing Modification and Toxicity Management Guidelines for Specific Immune-mediated Reactions for Durvalumab

Monotherapy (1 November 2017 Version)			
Adverse Event	Event Grade (CTCAE v. 4)	Dose Modifications	Toxicity Management
	Grade 3 (Isolated AST or ALT >8.0×ULN and ≤20.0×ULN, if normal at baseline) (Isolated AST or ALT >12.5×ULN and ≤20.0×ULN, if elevated >ULN at baseline)	 Hold study drug/study regimen dose until resolution to Grade ≤1 or baseline Resume study drug/study regimen if elevations downgrade to Grade ≤1 or baseline within 14 days and after completion of steroid taper. Permanently discontinue study drug/study regimen if the elevations do not downgrade to Grade ≤1 or baseline within 14 days Permanently discontinue study drug/study regimen for any case meeting Hy's law criteria, in the absence of any alternative cause.^b 	 For Grade 3: Regular and frequent checking of LFTs (e.g., every 1-2 days) until elevations of these are improving or resolved. Consult hepatologist (unless investigator is hepatologist); obtain abdominal ultrasound, including Doppler assessment of liver perfusion; and consider liver biopsy. Consider, as necessary, discussing with study physician. If investigator suspects toxicity to be immune-mediated, promptly initiate empiric IV methylprednisolone at 1 to 4 mg/kg/day or equivalent. If no improvement within 3 to 5 days despite 1 to 4 mg/kg/day methylprednisolone IV or equivalent, obtain liver biopsy (if it has not been done already) and promptly start treatment with immunosuppressive therapy (mycophenolate mofetil). Discuss with study physician if mycophenolate is not available. Infliximab should NOT be used. Once the patient is improving, gradually taper steroids over ≥28 days and consider prophylactic antibiotics, antifungals, and anti-PCP treatment (refer to current NCCN guidelines for treatment of cancer-related infections [Category 2B recommendation]).ⁱ
	Grade 4 (Isolated AST or ALT >20×ULN, whether normal or elevated at baseline)	• Permanently discontinue study drug/study regimen.	For Grade 4: Same as above (except would recommend obtaining liver biopsy early)
If transaminase rise is not isolated but (at any time) occurs in setting of either increasing total/direct bilirubin ($\geq 1.5 \times ULN$, if normal at			

Table 3: Dosing Modification and Toxicity Management Guidelines for Specific Immune-mediated Reactions for Durvalumab

baseline; or 2×baseline, if >ULN at baseline) or signs of DILI/liver decompensation (e.g., fever, elevated INR):

Manage dosing for Grade 1 transaminase rise as instructed for Grade 2 transaminase rise -

Manage dosing for Grade 2 transaminase rise as instructed for Grade 3 transaminase rise

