6.1. Dose Modifications

6.1.1. Dose Modifications and Toxicity Management for Durvalumab:

For adverse events (AEs) that are considered at least partly due to administration of durvalumab the following dose adjustment guidance may be applied:

- Treat each of the toxicities with maximum supportive care (including holding the agent suspected of causing the toxicity where required).
- If the symptoms promptly resolve with supportive care, consideration should be given to continuing the same dose of durvalumab along with appropriate continuing supportive care. If medically appropriate, dose modifications are permitted for durvalumab (see below).
- All dose modifications should be documented with clear reasoning and documentation of the approach taken.

In addition, there are certain circumstances in which durvalumab should be permanently discontinued.

Following the first dose of durvalumab, subsequent administration of durvalumab can be modified based on toxicities observed (see Tables 2, 3 and 4 below). Dose reductions are not permitted.

Based on the mechanism of action of durvalumab leading to T-cell activation and proliferation, there is the possibility of observing immune-mediated Adverse Events (imAEs) during the conduct of this study. Potential imAEs include immune-mediated enterocolitis, dermatitis, hepatitis, and endocrinopathies. Subjects should be monitored for signs and symptoms of imAEs. In the absence of an alternate etiology (e.g., infection or PD) signs or symptoms of enterocolitis, dermatitis, hepatitis, hepatitis, and endocrinopathy should be considered to be immune-related.

Dose modification recommendations and toxicity management guidelines for immune-mediated adverse events, for infusion-related reactions, and for non-immune-mediated adverse events are detailed in Tables 2, 3, and 4, respectively.

In addition, management guidelines for adverse events of special interest (AESIs) are detailed in Section 10.1.3. All toxicities will be graded according to NCI CTCAE v4.

Table 2 Dosing Modifications and Toxicity Management Guidelines for Immune-Mediated, Infusion Related,			
and Non Immune-mediated Reactions for Durvalumab Monotherapy (1 November 2017 Version)			
General Considerations			
Dose Modifications	Toxicity Management		

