 Grade 1 No dose modification Grade 2 Hold study drug/study regimen dose until grade 2 resolution to ≤ Grade 1 If toxicity worsens then treat as Grade 3 or Grade 4 Study drug/study regimen can be resumed once event stabilizes to Grade ≤1 after completion of steroid taper. Patients with endocrinopathies who may require prolonged or continued steroid replacement can be retreated with study drug/study regimen on the following conditions: The event stabilizes and is controlled. The patient is clinically stable as per Investigator or treating physician's clinical judgement. Doses of prednisone are at ≤10 mg/day or equivalent. Grade 3 Depending on the individual toxicity, may permanently discontinue study drug/study regimen Please refer to guidelines below 	 rule out any alternative etology (e.g., disease progression, concomitant medications, and infections) to a possible immune-mediated event. In the absence of a clear alternative etiology, all such events should be managed as if they were immune related. General recommendations follow. Symptomatic and topical therapy should be considered for low-grade (Grade 1 or 2, unless otherwise specified) events For persistent (greater than 3 to 5 days) low-grade (Grade 2) or severe (Grade ≥3) events, promptly start prednisone 1 to 2 mg/kg/day PO or IV equivalent. Some events with high likelihood for morbidity and/or mortality – e.g., myocarditis, or other similar events even if they are not currently noted in the guidelines – should progress rapidly to high dose IV corticosteroids 		
Grade 4 Permanently discontinue study drug/study regimen Note: For Grade 3 and above asymptomatic amylase or lipase levels hold study drug/regimen and if complete work up shows no evidence of pancreatitis, may continue or resume study drug/regimen	(methylprednisolone at 2 to 4 mg/kg/day) even if the event is Grade 2, and if clinical suspicion is high and/or there has been clinical confirmation. Consider, as necessary, discussing with the study physician, and promptly pursue specialist consultation.		
Note : Study drug/study regimen should be permanently discontinued in Grade 3 events with high likelihood for morbidity and/or mortality – e.g., myocarditis, or other	 If symptoms recur or worsen during corticosteroid tapering (28 days of taper), increase the corticosteroid dose (prednisone dose [e.g. up to 2-4 mg/kg/day PO or IV equivalent]) until stabilization or improvement of symptoms, 		

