Table 2 Dosing Modifications and Toxicity Management Guidelines for Immune-Mediated, Infusion Related,			
and Non Immune-mediated Reactions for Durvalumab Monotherapy (1 November 2017 Version)			
General Consideration	ns		
Dose Modifications	Toxicity Management		
similar events even if they are not currently noted in the guidelines. Similarly, consider whether study drug/study regimen should be permanently discontinued in Grade 2 events with high likelihood for morbidity and/or mortality – e.g., myocarditis, or other similar events even if they are not currently noted in the guidelines – when they do not rapidly improve to Grade <1 upon treatment with systemic steroids and following full taper. Note: There are some exceptions to permanent discontinuation of study drug for Grade 4 events (i.e., hyperthyroidism, hypothyroidism, Type 1 diabetes mellitus).	 then resume corticosteroid tapering at a slower rate (>28 days of taper). More potent immunosuppressives such as TNF inhibitors (eg, infliximab) (also refer to individual sections of the immune-related adverse event for specific type of immunosuppressive) should be considered for events not responding to systemic steroids. Progression to use of more potent immunosuppressives should proceed more rapidly in events with high likelihood for morbidity and/or mortality – e.g., myocarditis, or other similar events even if they are not currently noted in the guidelines – when these events are not responding to systemic steroids. With long-term steroid and other immunosuppressive use, consider need for Pneumocystis jirovecii pneumonia (PJP, formerly known as Pneumocystis carinii pneumonia) prophylaxis, gastrointestinal protection, and glucose monitoring. Discontinuation of study drug is not mandated for Grade 3 / Grade 4 inflammatory reactions attributed to local tumour response (e.g. inflammatory reaction at sites of metastatic disease and lymph nodes). Continuation of study drug in this situation should be based upon a benefit/risk analysis for that patient. 		
AE Adverse event; CTC Common Toxicity Criteria; CTCAE Common Terminology Criteria for Adverse	Events; imAE Immune-mediated adverse event; IV intravenous;		
INCL INduonal Cancer Institute; PO By mouth.			

Monotherapy (1 November 2017 Version)				
Adverse Event	Event Grade (CTCAE v. 4)	Dose Modifications	Toxicity Management	

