Endocrinopathy (e.g., hyperthyroidism, hypothyroidism, hypopituitarism, and adrenal insufficiency Type 1 diabetes mellitus, hypophysitis, exocrine event of amylase/lipase increased also included in this section)	Any Grade (depending on the type of endocrinopathy, refer to NCI CTCAE v4 for defining the CTC grade/severity)	General Guidance	 For Any Grade: Consider consulting an endocrinologist for endocrine events. Consider, as necessary, discussing with study sponsor-investigator (via the Big Ten CRC project manager). Monitor patients for signs and symptoms of endocrinopathies. Non-specific symptoms include headache, fatigue, behavior changes, changed mental status, vertigo, abdominal pain, unusual bowel habits, hypotension polydipsia, polyuria and weakness. Patients should be thoroughly evaluated to rule out any alternative etiology (e.g., disease progression including brain metastases, or infections). Depending on the suspected endocrinopathy monitor and evaluate thyroid function tests: TSH, free T₃ and free T₄ and other relevant endocrine and related labs (e.g., blood glucose and ketone levels, HgA1c).

Table 3: Dosing Monotherapy (1	Table 3: Dosing Modification and Toxicity Management Guidelines for Specific Immune-mediated Reactions for Durvalumab Monotherapy (1 November 2017 Version)		
Adverse Event	Event Grade (CTCAE v. 4)	Dose Modifications	Toxicity Management
			 For modest asymptomatic elevations in serum amylase and lipase, corticosteroid treatment is not indicated as long as there are no other signs or symptoms of pancreatic inflammation. If a patient experiences an AE that is thought to be possibly of autoimmune nature (e.g., thyroiditis, pancreatitis, hypophysitis, diabetes insipidus), the investigator should send a blood sample for appropriate autoimmune antibody testing

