		 Patients with endocrinopathies who may require prolonged or continued steroid replacement (e.g. adrenal insufficiency) can be retreated with study drug/study regimen on the following conditions: 1. The event stabilizes and is controlled. 2. The patient is clinically stable as per investigator or treating physician's clinical judgement. 3. Doses of prednisone are ≤10 mg/day or equivalent. 	 with appropriate diabetic therapy, without study drug/study regimen interruption, and without corticosteroids. For all patients with abnormal endocrine work up, except for those with isolated hypothyroidism, or Type I DM, and as guided by endocrinologist, consider short-term, corticosteroids (e.g., 1-2 mg/kg/day methylprednisolone or IV equivalent) and prompt initiation of treatment with relevant hormone replacement (e.g. hydrocortisone, or sex hormones). Once patients on steroids are improving, gradually taper immunosuppressive steroids (as appropriate and with guidance of endocrinologist) over ≥28 days and consider prophylactic antibiotics, antifungals and anti PJP treatment (please refer to current NCCN guidelines for treatment of cancer-related infections [Category 2B recommendation])ⁱ For patients with normal endocrine work up (lab or MRI scans), repeat labs/MRI as clinically indicated.
	Grade 3 or 4	For Grade 3 or 4 endocrinopathy other than hypothyroidism and Type 1 diabetes mellitus, hold study drug/study regimen dose until endocrinopathy symptom(s) are controlled Resume study drug/study regimen administration once event stabilizes and after completion of steroid taper. Patients with endocrinopathies who may require prolonged or continued steroid replacement (e.g., adrenal insufficiency) can be retreated with study drug/study regimen on the following conditions:	 For Grade 3 or 4: Consult endocrinologist to guide evaluation of endocrine function and, as indicated by suspected endocrinopathy and as clinically indicated, consider pituitary scan. Hospitalization recommended. For all patients with abnormal endocrine work up, except those with isolated hypothyroidism or Type 1 DM, and as guided by an endocrinologist, promptly initiate empiric IV methylprednisolone 1 to 2 mg/kg/day or equivalent, as well as relevant hormone replacement (e.g., hydrocortisone, sex hormones). Isolated hypothyroidism may be treated with replacement therapy without treatment interruption and without corticosteroids Isolated Type 1 diabetes mellitus may be treated with

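### Tables 2 and 3 give opposite re-dosing guidance after Grade 4 adrenal insufficiency, hypophysitis or hypopituitarism, and the protocol does not say which table governs

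*Combined protocol and SAP*

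**What the plan says.** Section 6.1.1 introduces its tables by saying that, for events at least partly due to durvalumab, "the following dose adjustment guidance may be applied".

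Table 2 (General Considerations) then sets out the action by grade:
- Grade 3: "Depending on the individual toxicity, may permanently discontinue study drug/study regimen Please refer to guidelines below".
- Grade 4: "Grade 4 Permanently discontinue study drug/study regimen".
- A later note in the same table: "There are some exceptions to permanent discontinuation of study drug for Grade 4 events (i.e., hyperthyroidism, hypothyroidism, Type 1 diabetes mellitus".

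Table 3 (specific immune-mediated reactions) has one row for endocrinopathies. Its label includes "hypothyroidism, hypopituitarism, and adrenal insufficiency Type 1 diabetes mellitus, hypophysitis". The Grade 3 or 4 cell of that row reads "For Grade 3 or 4 endocrinopathy other than hypothyroidism and Type 1 diabetes mellitus, hold study drug/study regimen dose until endocrinopathy symptom(s) are controlled", followed by "Resume study drug/study regimen administration once event stabilizes and after completion of steroid taper". The Grade 2 cell adds that patients who may "require prolonged or continued steroid replacement (e.g. adrenal insufficiency) can be retreated with study drug/study regimen" if the event is controlled, the patient is clinically stable and prednisone is at or below 10 mg/day or equivalent. The Grade 3 or 4 cell repeats that provision with the same three conditions and again gives adrenal insufficiency as the example.

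Two other rules bear on the same patients. Table 2 ends therapy if corticosteroids cannot be brought down to 10 mg/day of prednisone or less within 12 weeks of the last dose. Section 7.3 ends it if treatment is interrupted for 42 days or more because of a treatment-related event.

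**The concern.** The two tables sit a few pages apart in one section and are meant to be used together. For a Grade 4 event of the pituitary or adrenal gland, an investigator reading Table 2 finds a permanent stop, and one reading Table 3 finds a hold followed by resumption. The question they answer differently is whether to give more drug after a life-threatening event.

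These conditions are foreseen in the protocol. Section 10.8 lists adrenal insufficiency and hypophysitis/hypopituitarism among the identified risks of durvalumab monotherapy, and Section 11.1.4 lists them as adverse events of special interest. At stake are the safety of the affected patient, that patient's drug exposure, and the reason for discontinuation reported under Section 12.11.

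**Working it through.** No plan figure needs reproducing, because the point is a conflict of text. The check sets the two tables side by side, looks for a rule that ranks them, and asks how far other rules close the gap.

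**1. Side by side at Grade 4**

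| Event | Table 2 | Table 3, endocrinopathy row | Conflict on permanent discontinuation? |
|---|---|---|---|
| Hypothyroidism | Named exception | Treated without interruption | No |
| Type 1 diabetes | Named exception | Treated without interruption | No |
| Hyperthyroidism | Named exception | Hold, then resume | No |
| Adrenal insufficiency | Not an exception: permanent discontinuation | Hold, then resume; named as retreatable | Yes |
| Hypophysitis, hypopituitarism | Not an exception: permanent discontinuation | Hold, then resume | Yes |

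**2. Is there a ranking rule?** Table 2's Grade 3 entry sends the reader to the specific guidelines. Its Grade 4 entry does not. Neither Section 6.1.1 nor Section 7.3 says which table prevails. Table 2 also places its own provision for retreatment on steroid replacement under Grade 2, whereas Table 3 carries it at Grade 2 and at Grade 3 or 4.

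**3. Is this row unusual?** Yes. The Table 3 rows for pneumonitis, diarrhea/colitis, hepatitis, nephritis, rash, neurotoxicity, peripheral neuromotor syndromes and myocarditis all end in permanent discontinuation at Grade 4, as Table 2 does. The endocrinopathy row is where the tables part.

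**4. Do the other rules close the gap?** Only partly. Table 3 calls for a steroid taper of at least 28 days once the patient is improving. Against the 42-day limit in Section 7.3 this leaves 42 − 28 = 14 days. If interruption is counted from the start of the hold (an assumption, since the protocol does not define the start), a 28-day taper must begin in less than 14 days for dosing to resume in time. Slower cases end in discontinuation under either table. Faster cases do not, and patients on replacement steroids within the 10 mg/day limit may be retreated under Table 3. For both groups the tables still disagree.

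**5. How often could it arise?** Section 1.2.4.1 gives the only figures.
- Study 1108: 6 of 694 subjects had a treatment-related Grade 4 event. The terms listed are upper gastrointestinal hemorrhage, increased AST, dyspnea, neutropenia, colitis, diarrhea and pneumonitis; none is endocrine.
- ATLANTIC: no treatment-related Grade 4 event among 303 subjects.
- Together: 0 related Grade 4 endocrine events in 694 + 303 = 997 subjects. The rule-of-three upper 95% bound is 3/997 = 0.30%. Over 39 patients that is at most 39 × 0.0030 = about 0.12 expected cases.

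This assumes that rates in those advanced-disease populations, at their 2015 data cutoffs, carry over to this adjuvant setting.

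**6. What depends on it?** One-year relapse-free survival (Section 12.3) is defined without reference to treatment status. The sample size and replacement rule (Section 12.6) are untouched: patients who stop for toxicity are not replaced. The secondary endpoint (Section 12.4) is the occurrence and rate of adverse events, and its definition contains no discontinuation count. Reasons for discontinuation are reported under disposition (Section 12.11).

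**The case against.** The strongest reply is that the specific provision prevails over the general one. Table 2 is headed as general, Table 3 as specific, and the Table 3 cell is detailed enough to name adrenal insufficiency and set conditions. Table 2 also mentions discontinuation criteria in a table below, which could mean Table 3, though it could equally mean the grade list in Table 2 itself. This is a reasonable way to read the tables, but the protocol does not state it for Grade 4. Table 2 defers expressly at Grade 3 only, and it writes out its own Grade 4 exceptions, which would be needless if Table 3 simply overrode it.

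A second reply is that the endocrine exception list is not exhaustive despite its *i.e.*, because Table 2 makes other Grade 4 allowances: for asymptomatic amylase or lipase elevations, and for inflammatory reactions attributed to local tumour response. That is correct, but neither allowance reaches adrenal insufficiency, hypophysitis or hypopituitarism.

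Other parts of the reply stand. The tables are offered as guidance, so a reader who takes them as two binding orders goes further than Section 6.1.1 does. A reader might also infer that sites will in fact treat like patients differently. The documents do not show that: the endocrinopathy row suggests discussing cases with the sponsor-investigator, and Section 13.1 provides monthly meetings of all accruing sites that review significant toxicities. Divergence is possible, not established.

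**Conclusion.** The contradiction is real and limited to Grade 4 adrenal insufficiency, hypophysitis and hypopituitarism. Table 2's guidance is to stop permanently, Table 3's is to hold and resume, and nothing ranks them. Opposite re-dosing decisions are therefore open to investigators, except where the 42-day or 12-week rule ends therapy in any case.

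The expected frequency is low: no such related event appears in the figures given for 997 subjects, with an upper bound of about 0.12 cases in 39 patients under the assumption above. A reader might instead apply study 1108's 6 of 694 to this trial, but those events are of other types and do not measure this risk. A reader might also infer that the tolerability endpoint is distorted. Section 12.4 does not support that, although a patient who is re-dosed would be observed for longer under its on-drug-plus-30-days window.

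The point is worth correcting because of the consequence for the patient concerned, not because of any effect on the trial's efficacy conclusion. No view is taken here on which action is right.

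**What to change.** Reconcile the Grade 4 entry and exception note in Table 2 with the endocrinopathy row in Table 3, so that both name the same conditions with one action for each. Align the steroid-replacement retreatment provision, which Table 2 places under Grade 2 only. Add one sentence to Section 6.1.1 saying which table governs where a general and an event-specific entry differ. The medical lead decides the action for each condition.

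The cost is a wording change in two tables, with no added patients, visits or procedures. It still needs the approvals in Section 14.4 (sponsor-investigator, administrative headquarters, drug supplier and each site's IRB), so it could be carried in the next amendment if the medical lead judges that it can wait.

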	Grade 3 or 4 (Grade 3: AST or ALT >5-20 × ULN and/or T bili > 3.0-10 × ULN) Grade 4 (AST or ALT > 20 × ULN and/or T bili > 10 × ULN)	 For Grade 3: For elevations in transaminases ≤ 8 × ULN, or elevations in bilirubin ≤ 5 × ULN: - Hold study drug/study regimen dose until resolution to ≤ Grade 1 or baseline - Resume study drug/study regimen if elevations downgrade ≤ Grade 1 or baseline within 14 days and after completion of steroid taper - Permanently discontinue study drug/study regimen if the elevations do not downgrade to ≤ Grade 1 or baseline within 14 days For elevations in transaminases > 8 × ULN or elevations in bilirubin > 5 × ULN, discontinue study drug/study regimen. Permanently discontinue study drug/study regimen for any case meeting Hy's law criteria (AST and /or ALT > 3× ULN + bilirubin > 2× ULN without initial findings of cholestasis 	 For Grade 3 or 4: Promptly initiate empiric IV methylprednisolone at 1 to 4 mg/kg/day or equivalent. If still no improvement within 3-5 days despite 1 to 4 mg/kg/day methylprednisolone IV or equivalent, promptly start treatment with immunosuppressive therapy (mycophenolate mofetil). Discuss with study sponsor-investigator (via the Big Ten CRC project manager) if mycophenolate is not available. Infliximab should NOT be used. Hepatology consult, abdominal workup, and imaging as appropriate. Once improving, gradually taper steroids over ≥28 days and consider prophylactic antibiotics, antifungals and anti PJP treatment (please refer to current NCCN guidelines for treatment of cancer-related infections [Category 2B recommendation])ⁱ.

Table 3: Dosing Modification and Toxicity Management Guidelines for Specific Immune-mediated Reactions for Durvalumab				
Monotherapy (1 November 2017 Version)				
Adverse Event	Event Grade (CTCAE v. 4)	Dose Modifications	Toxicity Management	
		(i.e. elevated alkaline phos) and in the absence of any alternative cause ⁱⁱ For Grade 4: Permanently discontinue study drug/study regimen.		

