Hepatitis (elevated LFTs) Infliximab should not be used for management of immune-related hepatitis. See instructions at THIS shaded area is guidance only for management of "Hepatitis (elevated LFTs)" in HCC patients bottom of shaded area if transaminase rise is not isolated but (at any time) occurs in setting of either increasing bilirubin or signs of DILI/liver decompensation	Any Grade	General Guidance	 For Any Grade: Monitor and evaluate liver function test: AST, ALT, ALP, and TB. Evaluate for alternative etiologies (e.g., viral hepatitis, disease progression, concomitant medications, worsening of liver cirrhosis [e.g., portal vein thrombosis]). For HBV+ patients: evaluate quantitative HBV viral load, quantitative HBsAg, or HBeAg For HCV+ patients: evaluate quantitative HCV viral load Consider consulting hepatologist/Infectious disease specialist regarding change/implementation in/of antiviral medications for any patient with an elevated HBV viral load >2000 IU/ml Consider consulting hepatologist/Infectious disease specialist regarding change/implementation in/of antiviral HCV medications if HCV viral load increased by ≥2-fold For HCV+ with HBcAB+: Evaluate for both HBV and HCV as above 	

Monotherapy (1 November 2017 Version)			
Adverse Event	Event Grade (CTCAE v. 4)	Dose Modifications	Toxicity Management
	Grade 1 (Isolated AST or ALT >ULN and ≤5.0×ULN, whether normal or elevated at baseline)	 No dose modifications. If ALT/AST elevations represents significant worsening based on investigator assessment, then treat as Grade 2 event. For all grades, see instructions at bottom of shaded area if transaminase rise is not isolated but (at any time) occurs in setting of either increasing bilirubin or signs of DILI/liver decompensation 	

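### The two Grade 3 hepatitis branches in Table 3 overlap as worded, so some discordant transaminase and bilirubin values meet both hold-and-resume and discontinue

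*Combined protocol and SAP*

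**What the plan says.** The cell is in the combined protocol and SAP, section 6.1.1, Table 3, row Hepatitis (Elevated LFTs). A patient enters it under this definition: "Grade 3: AST or ALT >5-20 × ULN and/or T bili > 3.0-10 × ULN". Because of the and/or, one analyte at Grade 3 level is enough, whatever the other shows short of Grade 4.

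Inside the cell there are two branches:

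- Hold and resume: "For elevations in transaminases ≤ 8 × ULN, or elevations in bilirubin ≤ 5 × ULN". The actions are "Hold study drug/study regimen dose until resolution to ≤ Grade 1 or baseline" and then "Resume study drug/study regimen if elevations downgrade ≤ Grade 1 or baseline within 14 days and after completion of steroid taper". Failure to recover within 14 days means permanent discontinuation.
- Discontinue: "For elevations in transaminases > 8 × ULN or elevations in bilirubin > 5 × ULN, discontinue study drug/study regimen".

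A third sentence overrides both: "Permanently discontinue study drug/study regimen for any case meeting Hy's law criteria". The cell defines those criteria as AST and/or ALT above 3 × ULN plus bilirubin above 2 × ULN, with no initial cholestasis and no alternative cause.

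**The concern.** Two branches meant to divide Grade 3 patients should not share members. Here both conditions are joined by *or*. A patient with one analyte within its lower range and the other above its limit therefore satisfies both, and receives opposite instructions about restarting durvalumab.

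Two sites could apply the cell in good faith to identical laboratory values and act differently. That bears on patient safety, on drug exposure, on the toxicity and tolerability endpoint (section 12.4) and on the reasons for discontinuation to be summarised (section 12.11). It does not bear on the sample size or on the estimate of 1-year RFS.

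**Working it through.** The plan gives no figure to reproduce; this is mainly a check of logic.

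**Conditions as written** (T = transaminases, B = bilirubin, both × ULN; an elevation means above 1)

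- Hold: (1 < T ≤ 8) or (1 < B ≤ 5)
- Discontinue: (T > 8) or (B > 5)
- Hy's law limits: T > 3 and B > 2, with no cholestasis and no other cause

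**Single cases**

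| T | B | Grade 3 by | Hold | Discontinue | Above Hy's law limits |
|---|---|---|---|---|---|
| 10 | normal | T | no | yes | no |
| 10 | 1.8 | T | yes, by B | yes, by T | no |
| 2 | 6 | B | yes, by T | yes, by B | no (T ≤ 3) |

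With a normal bilirubin there is no bilirubin elevation and no conflict. The conflict needs both analytes raised.

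**Grid.** Take T in {1, 4, 6, 8, 8.1, 10, 15, 20} and B in {0.8, 1.2, 1.8, 2.0, 2.5, 3.5, 5, 5.1, 8, 10}. Of the 80 pairs, 10 are below Grade 3 (T of 1 or 4 with B ≤ 2.5), leaving 70.

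- Pairs meeting both branches: T in {4, 6, 8} with B in {5.1, 8, 10} gives 3 × 3 = 9. T in {8.1, 10, 15, 20} with B from 1.2 to 5 gives 4 × 6 = 24. Total 33 of 70.
- Setting aside every pair above the Hy's law limits leaves 4 × 3 = 12, all with T > 8 and B from 1.2 to 2.0. The grid has no T between 1 and 3, so the case T = 2, B = 6 is additional.
- Counting an analyte only when it is itself at Grade 3 level (T > 5, B > 3) gives 2 × 3 + 4 × 2 = 14 overlaps. All lie above the Hy's law limits.

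The counts depend on the grid chosen. They show where the overlap lies, not how often patients land there.

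**Possible tie-breakers elsewhere**

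- The general Grade 3 rule in Table 2 is "Depending on the individual toxicity, may permanently discontinue study drug/study regimen", and it then refers back to the specific guidelines.
- Table 3 has a rule for transaminase rises that are not isolated, but that block is "guidance only for management of 'Hepatitis (elevated LFTs)' in HCC patients".
- Section 11.2.4.2 uses the definition in section 11.1.4.3: ALT or AST above 3 × ULN with bilirubin above 2 × ULN. It requires interruption when no definitive diagnosis is found, and leaves continuation to the site investigator when an unrelated diagnosis is established. Neither example reaches it.

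**How many patients.** Section 1.2.4.1 gives related Grade 3 or higher events in Study 1108: AST in 7/694 and ALT in 5/694. For 39 patients:

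- AST: 39 × 7/694 = 0.39 expected
- ALT: 39 × 5/694 = 0.28 expected
- Overlap between the two groups is not given. If no subject had both, 39 × 12/694 = 0.67.

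These are rough ceilings for the transaminase-driven conflict. They include rises of 5 to 8 × ULN, isolated rises and Grade 4 events. For the bilirubin-driven case, raised bilirubin is absent from that section's list of such events seen in 3 or more subjects. If it was coded as its own term, that means at most 2/694, or 39 × 2/694 = 0.11.

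**The case against.** The best reply is that the cell should be read analyte by analyte within Grade 3: transaminases above 5 to 8 or bilirubin above 3 to 5 is hold, and anything higher is discontinue. A bilirubin of 1.8 × ULN is only Grade 2 and an ALT of 2 × ULN only Grade 1 in the same table, so neither would trigger the hold branch. The 14 overlaps left on this reading go to permanent discontinuation under Hy's law, unless there is cholestasis or another cause. A reader might equally let the stricter instruction govern. Both readings are sensible, and a reader should not infer that the conflict is unavoidable. But the documents state neither convention.

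Second, the branches may often end alike. Resuming needs recovery within 14 days and a completed steroid taper, which the cell sets at 28 days or more. Section 7.3 ends therapy after an interruption of 42 days or more for a treatment-related event. A taper begun on day 14 reaches 14 + 28 = 42 days, if interruption is counted from onset. This narrows the practical difference. It does not remove it, since recovery and taper may start earlier.

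Third, section 6.1.1 presents the dose adjustments as guidance that may be applied. This supports a low severity, but does not make two opposite instructions compatible.

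Two stronger inferences fail:

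- **Permanence.** The discontinue branch omits the word permanently, so a reader might infer that restart is left open. Table 2's general considerations describe the table's grade-based criteria as those for permanent discontinuation, and nothing offers a restart after discontinuation. At most this is an optional alignment of wording.
- **Frequency.** From the Study 1108 rates, the chance of at least one related Grade 3 or higher event among 39 is 1 − (1 − 7/694)^39 = 0.33 for AST and 1 − (1 − 5/694)^39 = 0.25 for ALT. A reader might take these as the chance of meeting the conflict. They cover any such event; the discordant ones are a smaller subset of unknown size. Study 1108 also enrolled advanced solid tumours, whereas these patients are resected and without recurrence.

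**Conclusion.** Wrong as written: an internal contradiction of minor severity. Read literally, the Grade 3 cell places some pairs of raised values in both branches, and no precedence rule exists. The part left unsettled is mainly transaminases above 8 × ULN with bilirubin above ULN up to 2 × ULN, and bilirubin above 5 × ULN with transaminases raised to no more than 3 × ULN. Higher pairs with cholestasis or another cause also fall outside the Hy's law sentence; section 11.2.4.2 leaves some of those to site judgement.

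The first group can be reached from an eligible baseline: section 3.1.9 admits bilirubin up to 1.5 × ULN, so a patient may already have a raised bilirubin when the transaminases climb.

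Expected numbers are a fraction of the 0.28 to 0.39 patients implied by each enzyme separately (0.67 if the two groups are distinct), assuming that Study 1108 rates carry over. For an affected patient the widest possible gap is 12 infusions (13 planned in section 5.2, less the first), and delay during a hold would shorten it. The conclusion rests on taking *elevation* to mean above ULN and *or* at face value.

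**What to change.** The sponsor-investigator and drug supplier should reconcile the two Grade 3 branches so that every pair of transaminase and bilirubin values falls in exactly one. They should decide which branch governs discordant values, and whether an analyte counts when it is not itself at Grade 3 level. This review takes no view on that choice. The revised wording can be checked against the grid above: no pair should meet both branches and none should meet neither. If the cell is being edited anyway, the wording for discontinuation could be aligned throughout.

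The cost is one or two sentences in Table 3, through the amendment route in section 14.4. No procedure, visit or analysis changes.
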